Pilot Study: A double-blind placebo-controlled pilot study investigated whether the nutritional supplement, Muscle Armor, affects immune function. Since inflammation is associated with loss of muscle during aging and wasting disease, it was hypothesized that Muscle Armor functions, in part, by exerting anti-inflammatory effects. It was also hypothesized that the supplement would boost the response to vaccination, the gold standard measure of immune function. Subjects were randomized to consume Muscle Armor (N=6) or placebo (N=6) for 4-weeks. The tetanus, diphtheria, and pertussis (TDAP) vaccine was administered two weeks after product consumption began. Plasma was collected prior to the start of consumption, immediately prior to vaccination, and 1- and 2-weeks post-vaccination. Muscle tissue was obtained before and after consumption of supplement or placebo though analyses of these specimens are not yet complete. Plasma C-reactive protein (CRP), tumor necrosis factor- α (TNF α), and interleukin-6 (IL6) were measured as systemic markers of inflammation.

Results and Conclusions for Inflammation: The results for CRP are shown in Figure 7. After 4-weeks of intervention, CRP levels decreased in the supplement group but not in the placebo group

(mean \pm SEM: -1.37 ± 1.06 versus 0.42 ± 0.50 mg/L). Based on analysis of log-transformed data, the difference between groups was not significant statistically ($P=0.16$). Although the sample size was relatively small ($N=12$), these data provide a reasonable estimate of the expected effect size which was calculated to be 0.85 standard deviations. This effect size is similar to the estimated effect size given for muscle macrophage content under Aim 1. Thus, the power for Aim 1 has been updated to include this new calculation. The proposed sample size ($N=50$ with 20% dropout) gives 80% power to detect an effect size of 0.85 or greater at a 5% significance level. The results for TNF α (not shown) also suggested that the supplement functions, in part, by decreasing systemic inflammation though a change in IL6 due to the supplement was not detected.

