Results and Conclusions for Vaccination: The results for the antibody response to the pertussis antigen are shown in Figure 8. Median levels of antibody increased in both groups after vaccination. The increase from pre-vaccination was greater in the supplement than the placebo group at both 1-week (37.8 v. 19.6) and 2-weeks (131.0 v. 70.7) post-vaccination. Based on a Mann-Whitney test, the difference between groups in the 2-week change in pertussis antibody titers was not statistically significant ($P=0.13$). Thus, it is unknown whether the proposed sample size ($N=50$ with 20% dropout) will allow detection of differences between supplement and placebo groups though the nonparametric test result based on only $N=12$ is suggestive that it may. Regardless, the measure remains valuable to the study because it is a good general measure of immune function that is quite variable for older adults. This variability is amenable to planned within group analyses to determine the correlation between immune function and muscle adaptation to training and detraining. This issue was previously addressed in the pitfalls section of the proposal is reiterated here due to its importance. The aims were purposefully designed to be independent so that conclusions can still be drawn for the relationships between immune function and training outcomes as well as supplementation and training outcomes even if immune function is not altered by supplementation.

[figure not shown]

Figure 7. Change in CRP levels after 4-weeks of consumption of Muscle Armor or placebo. Mean and standard error of change are shown.

[figure not shown]

Figure 8. Effects of Muscle Armor or placebo consumption on median response to the pertussis vaccine at 1- and 2-weeks post-vaccination.

RESEARCH DESIGN & METHODS

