STATISTICAL PLAN: The sample size (N=50) provides greater than 80% power for Aims 1-3 to detect mean differences between groups of 0.8 to 0.85 standard deviation (SD) units at a 5% level of significance. Power calculations were based on using a one-sided t-test to compare independent groups using data from our work and others [2;23;65] though non-parametric tests or transformations will be used as necessary for data containing outliers. There is no formal plan to adjust for multiple comparisons. However, multiple correlation analysis will be used to determine the correlation between endpoints and any possible inflation in the overall Type I error rate. This analysis will allow testing of the overall hypothesis that measures of immune function (Aim 1) will be positively correlated with adaptations to exercise (Aim 2) and retention of muscle strength, mass, and function after exercise training is halted (Aim 3). The hypotheses are stated for each aim and the time points for comparison are listed in Table 6.

Aim 1 Power: Aim 1 will determine if the supplement consumption for 2-weeks improves baseline measures of immune function or the immune responses to vaccination or acute exercise. The representative measures chosen to calculate power are change in muscle macrophage content after exercise (Finding 2) and change in CRP levels post-supplementation (Pilot Study Finding 1). Przybyla et al detected a 29% increase in CD163+ macrophages in young subjects after exercise but no change in older subjects [2]. Power for this aim is calculated to detect at least a 29% greater increase in macrophages in the supplement than the placebo group. Przybyla et al used a nonparametric test to lessen the effects of outliers. To be more conservative here, the calculations here dropped the most extreme high and low data values before estimating effect sizes. With that approach, the 29% increase corresponds to an effect size of 0.8 SD units (mean/SD = 0.128/0.159). Similar results were found using CRP data from Pilot Finding 1. The effect size for change in CRP is 0.85 SD units (mean/SD = 0.665/0.780 for log-transformed data). Having at least 20 subjects per group will provide 80% or greater power to detect a mean shift of 0.8-0.85 SD units at a significance level of 5% for the following Aim 1 hypotheses:

- a. The response to vaccination will be greater in the supplement than the placebo group. The change between times K and A (Table 6) will be compared between groups.

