- b. The resting ratio of CD4+ to CD8+ t-cells will increase in the supplement but not in the placebo group. The change between times G and C will be compared between groups.
- c. The change in t-cell subsets after acute exercise will be greater in the supplement than the placebo group. The change between times I and G will be compared to the change between times E and C for both groups.
- d. Resting cytokine levels will decrease in the supplement but not in the placebo group. Change will be compared between groups for blood (times G and C) and muscle (times H and D). *Similar results are predicted for the MuRF and MAFbx atrophy-related transcripts.*
- e. The increase in cytokine levels after acute exercise will be greater in the placebo group than the supplement group. For both groups, change between times I and G will be compared to the change

Table 6. Time points are lettered for clear reference by the stated hypotheses.	
BASELINE MEASURES (WEEKS 1-5)	
A.	Blood draw at study enrollment for measuring pre-vaccination antibody titers
B.	Assessment of muscle strength, mass, and function at baseline
C.	Blood drawn prior to acute exercise at baseline
D.	Muscle biopsy prior to acute exercise at baseline
E.	Blood drawn 1 hr after acute exercise at baseline
F.	Muscle biopsy 72 hrs after acute exercise at baseline
POST-SUPPLEMENT RUN-IN MEASURES (WEEK 8)	
G.	Blood drawn prior to acute exercise after 2-weeks of supplementation
H.	Muscle biopsy prior to acute exercise after 2-weeks of supplementation
I.	Blood drawn 1 hr after acute exercise after 2-weeks of supplementation
J.	Muscle biopsy 72 hrs after acute exercise after 2-weeks of supplementation
MEASURES DURING TRAINING PERIOD (WEEKS 9-20)	
K.	Blood draws at weeks 1 and 2 post-vaccination for measuring antibody response
POST-TRAINING MEASURES (WEEK 21)	
L.	Assessment of muscle strength, mass, and function after completion of training
M.	Muscle biopsy 72 hrs after final exercise bout of training
MEASURES DURING POST-TRAINING FOLLOW-UP (WEEKS 22-4)	
N.	Assessments of strength, mass, and function after 16 and 26 weeks of detraining

between E and C for blood, and for muscle the change between times J and H will be compared to the change between times F and D.

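### The plan lets outliers in the outcome data decide between t-test, transformation and rank test, with no rule, and fixes neither the scale nor the deciding draw for the vaccine-response hypothesis (Aim 1, hypothesis a)

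*Combined protocol and SAP*

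**What the plan says.** The opening paragraph of the Statistical Plan states "Power calculations were based on using a one-sided t-test to compare independent groups", "at a 5% level of significance", and adds in the same sentence as the t-test that "non-parametric tests or transformations will be used as necessary for data containing outliers". It has no formal adjustment for multiple comparisons.

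Under Aim 1 Power, at least 20 subjects per group are said to give 80% power or more for a shift of 0.8 to 0.85 SD. The list of hypotheses this covers begins with the vaccine response (hypothesis a). For that one, "The change between times K and A (Table 6) will be compared between groups". Table 6 defines time K as "Blood draws at weeks 1 and 2 post-vaccination for measuring antibody response", which is two draws. Time A is the enrolment draw. The Response to Vaccination section makes pertussis the antigen of main interest but sets no scale and no deciding draw.

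The pilot results show how such data have been handled. For CRP, "Based on analysis of log-transformed data, the difference between groups was not significant statistically". For pertussis, the median increases were greater with supplement at "1-week (37.8 v. 19.6) and 2-weeks (131.0 v. 70.7) post-vaccination", and the 2-week change was compared by Mann-Whitney (P=0.13, N=12). The same paragraph says it is not known whether the planned sample size can detect a group difference in vaccine response.

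**The concern.** The clause makes the form of the test depend on the data being tested. The trial is double-blind, so the choice could be made blind, but nothing requires that. If several defensible tests can be run and one reported, the nominal 5% no longer describes the procedure. The Laboratory Aspects section adds to the freedom, because it lets an immune measure and its hypothesis change without this counting as a deviation.

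Hypothesis a is the most exposed. Change could mean a raw difference, a log ratio or a fold rise, at either draw or both. Titres are usually skewed, and the protocol calls this measure highly variable in older adults. On raw change, a few subjects with high prior titres can dominate the variance, and ranking raw changes does not remove the dependence on prior titre. At stake are the credibility of a positive result on the measure the protocol treats as the gold standard of immune function, and the 80% power claimed for it.

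**Working it through.** **1. The plan's own figure.** Inputs (Statistical Plan): n = 20 per group, one-sided 5%, d = 0.8 to 0.85. The sources are 0.128/0.159 = 0.805 (macrophages, extremes dropped) and 0.665/0.780 = 0.853 (log CRP). With a noncentral t on 38 degrees of freedom and noncentrality d × √(20/2):

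- d = 0.80: 0.80 × 3.162 = 2.530, power 79.9%
- d = 0.85: 0.85 × 3.162 = 2.688, power 84.0%

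The stated 80% is reproduced, and only as a one-sided figure (two-sided: 69.3% and 74.5%). Neither source is a titre.

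**2. What the pilot says about scale.** Ratios of median increase: 37.8/19.6 = 1.93 at 1 week and 131.0/70.7 = 1.85 at 2 weeks. Raw gaps: 37.8 − 19.6 = 18.2 and 131.0 − 70.7 = 60.3. A stable ratio with a growing gap is suggestive of a multiplicative effect, no more.

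**3. Power for hypothesis a by choice of test.** Assumptions, none of them in the documents:

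- titres are log-normal;
- the median rise is 8-fold;
- the log SD of prior titre is 0.5, 0.8 or 1.1;
- the arms differ by a factor of 1.85 in fold rise, borrowed from the pilot's ratio of median increases;
- the SD of the log rise is ln(1.853)/0.8 = 0.617/0.8 = 0.77.

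The last choice makes the effect exactly 0.8 SD on the log scale, so 80% for the log-rise t-test holds by construction. Simulated power, 20 per arm, one-sided 5%:

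| Correlation of log rise with prior titre | Test | SD 0.5 | SD 0.8 | SD 1.1 |
|---|---|---|---|---|
| 0 | t-test, raw change | 57% | 42% | 30% |
| 0 | Mann-Whitney, raw change | 67% | 55% | 44% |
| 0 | t-test, log rise | 80% | 80% | 80% |
| −0.5 | t-test, raw change | 82% | 73% | 56% |
| −0.5 | Mann-Whitney, raw change | 86% | 80% | 69% |
| −0.5 | t-test, log rise | 78–80% | 78–80% | 78–80% |

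Repeat runs differ by a point or two. A comparison of log titre adjusted for log baseline titre held 78–96% in every scenario run. It was at most about 1 point below the log-rise test and never materially below the rank test.

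**4. How far the 80% depends on the unknown SD.** Treat the change itself as log-normal with the pilot's 2-week medians. A t-test on its log then has 99% power at a log SD of 0.5 (0.617/0.5 = 1.23 SD), 80% at 0.77 and 60% at 1.0 (0.617 SD).

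**5. False-positive rate with no effect, one draw, one-sided 5%.**

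- Raw-change t-test fixed in advance: 3.7–4.9%.
- Mechanical switch when a 1.5-IQR rule flags an outlier: 4.5–6.0% over all runs. The rule fires in 84% to over 99% of simulated titre trials.
- Smallest P of raw t, log t and Mann-Whitney: about 8–11% for prior-titre log SD 0.5 to 1.1, and 6.7–10.8% over a wider grid that includes no spread in prior titre.

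**The case against.** A reader might infer that the plan prescribes a t-test on raw change for titres. It does not. The t-test is named as the basis of the power calculation, the same sentence allows transformation and ranks, and the pilot used Mann-Whitney for titres. Since an outlier rule would nearly always fire on such data, the raw t-test would seldom be the test used.

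A reader might also infer that the trial's 5% error is inflated. That follows only if the most favourable result is picked, which the text does not propose. A consistently applied switch stays near 5%. Using both draws could add to the error, but that is multiplicity, which the plan openly leaves unadjusted, and the Vaccination section gives a reason for the second draw (a possibly delayed response).

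The ranking of methods is not settled either. With a correlation of −0.5 and a prior-titre SD of 0.5, Mann-Whitney on raw change (86%) beats the log-rise t-test. If the change itself is log-normal at the pilot medians with log SD 0.77, the figures are 78% for Mann-Whitney and 80% for the log t-test. The stable pilot ratio comes from the same six subjects per arm at two times, with no spread given. Dropping macrophage extremes was a step in estimating an effect size, not an outcome test, so it is weak evidence of inconsistent practice.

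All of this stands, and it limits the size of the problem. It does not supply the missing rule, scale or deciding draw.

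**Conclusion.** The concern holds as a gap in pre-specification with a measurable but conditional cost. The choice of test is left to the outcome data without criterion, order or timing, and hypothesis a has no stated scale and no deciding draw. The error rate could reach about 8–11% at one draw as an upper bound. Power on raw change could be as low as about 29% (t-test) or 43% (Mann-Whitney) if titres are log-normal, prior titres vary widely and the log rise is independent of them. With a negative correlation the loss is smaller or absent. The documents give no titre SD or correlation, so no single power figure can be defended.

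One part needs no simulation. The Statistical Plan places hypothesis a under 80% power, while the pilot discussion says detectability of a vaccine difference is unknown. The 80% therefore has no titre-based support. The point should be addressed, but it does not invalidate the design.

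**What to change.** Add a paragraph to the Statistical Plan, settled before any comparison by arm:

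- Name one scale and one test for each endpoint, and delete the open-ended outlier clause.
- For hypothesis a, compare log pertussis titre at the 2-week draw (the one tested in the pilot) between arms, adjusted for log titre at time A. Make the 1-week draw supportive and Mann-Whitney a named sensitivity analysis.
- Keep CRP on the log scale already used for its effect size.
- For other laboratory measures, fix the scale from blinded pooled data or earlier data, with a rule for zero or undetectable values. The documents do not support a blanket log rule for cell counts, phosphorylation ratios or CD4:CD8.
- Restate the 80% for hypothesis a as conditional on a 0.8 SD effect on the chosen scale, and reconcile it with the pilot discussion.

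The cost is that paragraph, the loss of freedom to switch tests, and effects on log-analysed measures reported as geometric-mean ratios. No extra subjects, samples or assays are needed.

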- A. **Response to Vaccination:** β -hydroxy- β -methylbutyrate has been used in animal science to improve the response to vaccination [32]. The study will determine if 2-weeks of supplementation improves the response of older adults to the TDAP vaccine. The response to *pertussis* is of primary interest though the responses to the tetanus and diphtheria antigens will also be measured. Serum antibody titers will be compared between pre-vaccination and two time points post-vaccination. Enzyme-linked immunosorbent assays are available for measuring antibodies to each antigen (IBL International, Toronto, Ontario).
- B. **T-Cell Subpopulations:** Glutamine and arginine may be conditionally essential amino acids in the contexts of aging and exercise that are needed for optimal T-Cell function [34;56]. Aging decreases the ratio of naïve helper (CD4+) to cytotoxic (CD8+) T-Cells [57]; and though the levels of both cell populations increase shortly after moderate exercise for older adults, their levels do not reach the pre-exercise levels of young adults [58]. The proposed study will determine if 2-weeks of supplementation increases the CD4+ to CD8+ ratio or increases the response to acute exercise. A regulatory t-cell subset (CD4+, CD25+, FoxP3+) will also be examined since these cells function as regulators of immune function that prevent an uncontrolled immune response or autoimmunity [59]. Assessment of T-cell subsets will be carried out by flow cytometry using fluorochrome-linked antibodies specific to each marker (BD Biosciences, San Jose, CA). Additionally, if an alteration in inflammatory status is indicated by the cytokine analysis, then the Th17 subset (CD4+, CCR6+, CD161+, ROR α +) will be evaluated. This pro-inflammatory subset has not been studied following supplementation or exercise and the results could provide for the first time information on whether alteration in Th17 t-cells accompanies improvement in immune status.

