- f. The proliferative capacity of peripheral blood mononuclear cells will be greater in the supplement than the placebo group. The change between times G and C will be compared between groups. The change between times I and E will also be compared between groups.
- g. The resting number of muscle CD163+ macrophages will increase in the supplement but not in the placebo group. The change between times H and D will be compared between groups.
- h. The number of muscle CD163+ macrophages will increase after acute exercise in the supplement but not in the placebo group. The change between times J and H will be compared to change between times F and D for both groups.
- i. Resting NFkB activity will decrease and PI3K activity will increase in the supplement group but not in the placebo group. The change between time points H and D will be compared between groups.
- j. In response to acute exercise, NFkB activity will be lower and PI3K activity will be greater in the supplement group than in the placebo group. The change between times J and H will be compared to change between times F and D for both groups. *Responses similar to NFkB are predicted for FOXO1, and responses similar to PI3K are expected for STAT3, AKT, P38 MAPK, and ERK 1 and 2.*

Aim 2 Power: Aim 2 will determine whether supplement consumption increases muscle adaptation to 12-weeks of resistance training. The representative response measure for this objective is post-training percent increase in muscle strength. In a similar study, Trappe et al sought to improve strength gain by resistance training plus drug treatment. The drug treatment group gained significantly more strength by 25.1% than the group receiving placebo (26.4% vs. 21.1%, $P<0.05$) [23]. The previous findings presented here (Finding 4) indicate that older subjects completing a 12-week training program but not taking supplements will experience an average strength gain of $25 \pm 8\%$. If treatment with the proposed supplement improves strength similarly to the Trappe drug treatment, subjects in the supplement group will improve strength by an average of 31% (i.e., 25.1% greater than those of the placebo group). This translates to an approximate effect size of 0.8 SD units ($0.25*0.251/0.08$) if variances are pooled for the groups compared. With 20 subjects per group, there will be 80% power to detect a mean shift of 0.8 SD units using a significance level of 5% for the Aim 2 hypotheses:

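### Nineteen lettered hypotheses share a 5% level with no primary endpoint and no multiplicity adjustment, and the correlation analysis offered in its place cannot control the type I error

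*Combined protocol and SAP*

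**What the plan says.** The Statistical Plan sets out hypotheses 1a to 1j, 2a to 2f and 3a to 3c. It claims more than 80% power for all three aims to detect "mean differences between groups of 0.8 to 0.85 standard deviation (SD) units at a 5% level of significance", and each aim's power paragraph attaches the 5% level to that aim's whole list. On multiplicity it says "There is no formal plan to adjust for multiple comparisons", and continues that "multiple correlation analysis will be used to determine the correlation between endpoints and any possible inflation in the overall Type I error rate". The same analysis has a second job: "This analysis will allow testing of the overall hypothesis that measures of immune function (Aim 1) will be positively correlated" with the training and retention outcomes.

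No endpoint is called primary for the trial or for an aim. The nearest statements are these:

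- The power paragraphs use representative measures: CD163+ macrophage change after exercise and CRP change for Aim 1, strength gain for Aim 2 ("The representative response measure for this objective is post-training percent increase in muscle strength"), and retained strength gain for Aim 3.
- Blood Measures, item A, puts pertussis ahead of tetanus and diphtheria, then adds "Serum antibody titers will be compared between pre-vaccination and two time points post-vaccination".
- Muscle Measures, item F, gives priority to IL1β, IL10 and IGF1 within the gene-expression assays, and item H picks out some signalling factors.

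On sidedness the plan says only "Power calculations were based on using a one-sided t-test to compare independent groups".

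**The concern.** When many hypotheses share one unadjusted level and none is designated primary, any of them that reaches P<0.05 can be reported as the finding that the supplement works. The plan recognises the problem, but its remedy does not address it. Correlating endpoints describes their dependence; it changes no P value, sets no threshold and leads to no decision.

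The family is also larger than 19 and not closed:

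- 1a covers three antigens and two post-vaccination draws.
- 1d and 1e cover several cytokines in blood and in muscle.
- 1f contains two comparisons, and 1i and 1j cover several signalling factors.
- Strength is tested on three exercises and function by four tests.
- Time N in Table 6 includes assessments at 16 and at 26 weeks.
- The Study Outcomes paragraph under Laboratory Aspects lets an immune measure and its hypothesis change without this counting as a deviation.

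At stake is whether a reader of the results can separate a planned key comparison from the most favourable of many.

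**Working it through.** **Inputs from the Statistical Plan.** Hypotheses: 10 + 6 + 3 = 19. Level: 5%. Evaluable subjects: 20 per group ("Having at least 20 subjects per group will provide 80% or greater power"). Effect sizes: 0.128/0.159 = 0.805 and 0.665/0.780 = 0.853 (Aim 1); 0.25 × 0.251/0.08 = 0.784, rounded to 0.8 (Aim 2); 0.8 by assumption (Aim 3). With 20% dropout, 40/0.80 = 50 enrolled.

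**The plan's own power.** Two-sample t-test, noncentral t with 38 degrees of freedom, 20 per group:

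| Effect (SD) | One-sided 5% | Two-sided 5% |
|---|---|---|
| 0.80 | 79.9% | 69.3% |
| 0.85 | 84.0% | 74.5% |

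The stated 80% reproduces one-sided, to rounding, and does not reproduce two-sided. This, with the directional wording of the hypotheses, is the basis for inferring one-sided final tests.

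**Family-wise error, independent tests, all nulls true:** 1 − 0.95^k.

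| Family | k | Chance of at least one false positive |
|---|---|---|
| Aim 1 | 10 | 1 − 0.95^10 = 40.1% |
| Aim 2 | 6 | 1 − 0.95^6 = 26.5% |
| Aim 3 | 3 | 1 − 0.95^3 = 14.3% |
| All | 19 | 1 − 0.95^19 = 62.3% |

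The expected number of false positives over 19 tests is 19 × 0.05 = 0.95, whatever the correlation.

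**Allowing for dependence.** The documents give no correlations between endpoints, so a common value is assumed. Simulating 19 equally correlated normal statistics, each tested at one-sided 5%, gives:

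| Assumed correlation | 0 | 0.1 | 0.3 | 0.5 | 0.7 | 0.9 | 1 |
|---|---|---|---|---|---|---|---|
| Family-wise error | 62% | 55% | 44% | 33% | 24% | 14% | 5% |

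Only at correlation 1 does the error return to 5%.

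**Cost of the ways to control it** (20 per group, 0.8 SD, one-sided):

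- One primary per aim, each at 5%: power 79.9% for each, N=50. Error across the three, if independent, is 1 − 0.95^3 = 14.3%.
- One primary per aim with the level split, 0.05/3 = 0.0167: power 62.8%. Keeping 80% needs 29 per group, or 58/0.80 = 72.5, so 73 enrolled.
- Bonferroni over all 19, 0.05/19 = 0.00263: power 34.9%. Keeping 80% needs 44 per group, or 88/0.80 = 110 enrolled.

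**The case against.** The strongest defence is that this is a 50-person mechanistic trial which openly declares that it does not adjust, whose aims were built to stand apart (Results and Conclusions for Vaccination, under Preliminary Studies), and which already ranks some measures. Much of this is fair. The per-aim figures of 40%, 26% and 14% describe the design better than the pooled 62%, and control within each aim is a defensible choice. But the results are not labelled exploratory: the Abstract presents the hypotheses as tests with 80% power.

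A reader might draw four stronger conclusions that the documents do not support:

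- *That the plan declares one-sided final tests.* It states sidedness only for the power calculations. If the final tests were two-sided 5%, the independent-test figures for any false positive would be the same, but the chance of one favouring the supplement over 19 tests would be 1 − 0.975^19 = 38%.
- *That correlations say nothing about the inflation.* Dependence is what moves the figure from 62% to 14% in the table above, so correlations could feed an estimate of it. What is missing is the method and any rule that follows from it. Estimating the inflation afterwards is still not control.
- *That the vaccine response is six equal tests, with 26% error.* Pertussis is already placed first, which leaves two draws: 1 − 0.95^2 = 9.75% if independent, and less for repeat titres in the same people. Only the key week is open.
- *That nothing marks a key result.* The representative measures and the priority antigens and transcripts do so informally. They fall short of a designated primary, and Aim 1 has two representative measures.

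**Conclusion.** The concern holds. The plan tests at least 19 hypotheses at 5% with no primary and no adjustment, and its substitute cannot control the type I error. The size is 40%, 26% and 14% by aim and 62% overall if tests are independent and all nulls are true, or about 55% to 14% overall for an assumed common correlation of 0.1 to 0.9. These figures count each letter as one test, so for a given correlation they understate the family as written. One-sided testing is an inference from the power calculation. The defect affects how results may be interpreted and does not undermine the sample size. It should be corrected before the data are unblinded.

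**What to change.** Amend the Statistical Plan as follows.

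1. **Name one primary per aim from the representative measures.**
   - Aim 1: the CD163+ macrophage response to acute exercise (hypothesis 1h). State that it is chosen over CRP, which has no lettered hypothesis.
   - Aim 2: change in strength from B to L, for one named lift or a prespecified composite. Figure 5 reports knee extension, but the Aim 2 power paragraph does not say which lift its 25% gain refers to.
   - Aim 3: change in the same strength measure from L to the 26-week assessment at N.
2. **Fix the key vaccine comparison.** Keep pertussis as the leading antigen and add that week 2 is the key time.
3. **Label everything else** secondary or exploratory. A false-discovery-rate column within each aim is optional.
4. **State the error policy.** Error is held at 5% within each aim, in line with the aims being designed to be independent. Disclose that up to 14.3% remains across the three primaries if they are independent. Also declare the sidedness of the final tests.
5. **Reword the correlation sentence.** Describe the analysis as testing the immune-muscle hypothesis and, at most, describing dependence between endpoints, not as a safeguard on type I error.

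The cost is wording. With one primary per aim at one-sided 5%, N=50 and the plan's stated power stand; splitting the level three ways instead would cut power at 0.8 SD to about 63%. The real price is that non-primary results can no longer be presented as confirmatory.
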